## Protocol Amendment Summary of Changes Table

PROTOCOL HISTORY		
Document	Date	Amendment Type
SA 3	19-Jul-2021	Substantial
SA 2	22-Feb-2021	Substantial
NSA 1	09-Dec-2020	Non-substantial
Original Protocol	02-Dec-2020	N/A

### Amendment NSA 1 09-Dec-2021

#### Overall Rationale for the Amendment:

Section # and Name	Description of Change	Brief Rationale
Inclusion Criteria	Update to inclusion criteria	Administrative error
Overall document	Minor administrative corrections	Administrative error

### Amendment SA 2 16-Feb-2021

#### Overall Rationale for the Amendment:

Section # and Name	Description of Change	Brief Rationale
2.2 Exclusion	Exclusion criterion 27	Brought in line with main protocol
3 Screening Process	7-day isolation and 72 hours PCR test	Stay at home for 7 days required prior to quarantine to follow pre-admission infection control procedure agreed with the RFH. PCR test required 72 hours prior to admission.
4.1.2 Ethics	Corrected typographical error	HRA approval is not required for either screening or main protocol as there are no NHS trusts involved in the study.
4.1.2 Ethics	Corrected typographical error	CCC is not required for either screening or main protocol as there are no NHS trusts involved in the study.
4.1.3 Consent	Remote consent	Participants screened prior to implementation of this amendment will require re-consenting. The process for this has been described.
4.1.8 Audits	Corrected typographical error	Removed reference to imperial college healthcare NHS trust as sponsor. ICL is the sponsor only.

## Amendment SA 3 19 Jul 2021

## Overall Rationale for the Amendment:

Section # and Name	Description of Change	Brief Rationale
2.1.3 Inclusion Criteria	Change to wording – removal of Sero-negative to Sero-suitable subjects	Wording changed to reflect the purpose of the Extension Phase of the current protocol – to include previously vaccinated subjects.
2.1.4 Inclusion Criteria	Change to contraception wording for women.	Extension of time for contraception post-viral challenge – wording changed from 30 days to 6 months after receipt of study virus.
2.1.5 Inclusion Criteria	Change to contraception wording for men.	Extension of time for contraception post-viral challenge – wording changed from 30 days to 6 months after receipt of study virus.
2.1.8 Inclusion Criteria	Removal of QCOVID tool wording – adding requirement of evidence of completed COVID-19 vaccination course	Evidence required that subjects have received both doses of COVID-19 vaccine.
2.2.3 Exclusion Criteria	Addition of wording	No previous SARS-Cov-2 infection.
2.2.12 Exclusion Criteria	Removal of wording Hb1A1C	Hb1A1C – will be ‘optional’ as random glucose also recorded.
2.2.17 Exclusion Criteria	Removal of wording stating, ‘no travel restrictions post D28 follow-up.’	Precaution to advise subjects to restrict travel should they be re-infected by D28
2.3 Personalised risk assessment using the QCOVID tool	Removal of Section.	QCOVID – no longer part of exclusion criteria.
3 Screening Process	Include new wording for volunteer identification	Use of ethically-approved volunteer database if available.
3 Screening Process	Include new wording for assessing inclusion/exclusion criteria	Inclusion/exclusion criteria at screening will be assessed based on available evidence
3 Screening Process	7-day isolation amended to ‘up to’ 7-day isolation	Brought in line with main protocol and main PIS-ICF, able to follow current restrictions in place at the Quarantine Unit
4.1.8 Audits	Corrected typographical error.	Corrected wording.
4.2 Appendix 2	Corrected typographical error	Typographical error in email address corrected

4.4 Appendix 4	Table of toxicity grading scale replaced	Brought in line with main protocol
----------------	--	------------------------------------

## 1. Introduction

The aim of this screening protocol is to assess volunteers for their potential eligibility to participate in a dose finding human experimental infection study in healthy subjects using a GMP-produced SARS-CoV-2 wild type strain.

## 2. Study Population

Recruitment will be done through a number of channels:

- Approved advertising, including social media
- hVIVO volunteer database
- Referral
- Organic search, i.e. where the volunteer has learned of this study by doing a Google search or through friends or family rather than due to any advertising

Following Research Ethics Committee approval of the full study, screened subjects who confirm their willingness to participate in the SARS-CoV-2 human infection challenge characterization study will be invited to consider the study-specific PIS-ICF and enter the final study consenting process.

The number of subjects who are to be recruited will depend on specific sample-size requirements for the SARS-CoV-2 human infection characterization study.

### 2.1. Inclusion Criteria

The main inclusion criteria for the SARS-CoV-2 challenge study are listed below.

NO	INCLUSION CRITERIA
1	An informed consent document signed and dated by the participant and the Investigator.
2	Male or female, age between 18 and 30 years inclusive (at the time of the study consent)
3	Sero-suitable i.e. with evidence of SARS-CoV-2 vaccine-induced antibody responses but no evidence of previous SARS-CoV-2 infection by an authorised serology test. Those with indeterminate levels and no history of laboratory-confirmed SARS-CoV-2 infection may be included or excluded at the PI's discretion on a case-by-case basis.
4	Women of childbearing potential with a documented menstrual period within 28 days before the first dose (unless using a contraceptive method that suppressed menstruation as indicated in the study protocol) and willing and able to use contraception as described in the study protocol from 2 weeks before the scheduled date of viral challenge until 6 months after receipt of the final dose of study virus or intervention treatment (whichever occurs last). Negative urine pregnancy test will be required at screening plus, on admission to the quarantine unit, a Negative serum beta human chorionic gonadotropin ( $\beta$ -hCG) is a required. A negative urinary pregnancy test prior to virus challenge is also required.
5	Men who are willing to use one of the contraception methods described in the study protocol, from the time of the date of viral challenge, until 6 months after receipt of the final dose of study medication.

6	In good health with no history of clinically significant medical conditions (as described in Exclusion criteria) that would interfere with subject safety, as defined by medical history, physical examination and routine laboratory tests, ECG, and Chest X-Ray* and determined by the Investigator at a screening evaluation and/or at admission to the Quarantine Unit.
7	Subjects will have a documented medical history either prior to entering the study and/or following medical history review with the study physician at screening
8	Evidence of having had a complete COVID-19 vaccination course (as one or two intramuscular injections depending on the authorisation schedule) with the last injection at least 14 days before enrolment
9	Willing and able to commit to participation in the study

\* No radiological assessments will be conducted as part of this screening process. Chest X-Ray may only be performed after volunteer signs main PIS-ICF.

## 2.2. Exclusion criteria

The main exclusion criteria for the SARS-CoV-2 challenge study are listed below.

NO	STANDARD EXCLUSION CRITERIA
Any potential subject who meet any of the criteria below will be excluded from participating in this study.	
Clinical history	
1.	
History or evidence of any clinically significant or currently active cardiovascular, (including thromboembolic events), respiratory, dermatological, gastrointestinal, endocrine, haematological, hepatic, immunological, rheumatological, metabolic, urological, renal, neurological, psychiatric illness. Specifically:
 
a) Subjects with any history of physician diagnosed and/or objective test confirmed asthma, chronic obstructive pulmonary disease, pulmonary hypertension, reactive airway disease, or chronic lung condition of any aetiology or who have experienced:
 
 
o Significant/severe wheeze in the past
 
o Respiratory symptoms including wheeze which has ever resulted in hospitalisation
 
o Known bronchial hyperreactivity to viruses
 

NO	STANDARD EXCLUSION CRITERIA
	

b) History of thromboembolic, cardiovascular or cerebrovascular disease

c) History or evidence of diabetes mellitus

d) Any concurrent serious illness including history of malignancy that could interfere with the aims of the study or a subject completing the study. Basal cell carcinoma within 5 years of treatment or with evidence of recurrence is also an exclusion

e) Migraine with associated neurological symptoms such as hemiplegia or vision loss. Cluster headache/migraine or prophylactic treatment for migraine

f) History or evidence of autoimmune disease or known immunodeficiency of any cause.

g) Other major disease that, in the opinion of the Investigator, could interfere with a subject completing the study and necessary investigations.

h) Immunosuppression of any type.

2.	Any significant abnormality altering the anatomy of the nose in a substantial way or nasopharynx, a clinically significant history of epistaxis (large nosebleeds) within the last 3 months, nasal or sinus surgery within 6 months of inoculation.
3.	Clinically active rhinitis (including hay fever) or history of moderate to severe rhinitis, or history of seasonal allergic rhinitis likely to be active at the time of inclusion into the study and/or requiring regular nasal corticosteroids on an at least weekly basis, within 30 days of admission to quarantine.
4.	History of anaphylaxis and/or a history of severe allergic reaction or significant intolerance to any food or drug, as assessed by the PI.
5.	History or presence of alcohol addiction, or excessive use of alcohol (average weekly intake in excess of 28 units alcohol; one unit being a half glass of beer, a small glass of wine or a measure of spirits).
6.	Psychiatric illness including subjects with a history of depression and/or anxiety with associated severe psychiatric comorbidities, for example psychosis. Specifically, 

a) Subjects with history of anxiety-related symptoms of any severity within the last 2 years if the Generalized Anxiety Disorder-7 score is <math>\geq 4</math>

b) Subjects with a history of depression of any severity within the last 2 years if the Patient Health Questionnaire-9 score is <math>\geq 4</math>

7.	Current smokers or subjects who have smoked $\geq 5$ pack years at any time [5 pack years is equivalent to one pack of 20 cigarettes a day for 5 years]. 

• Subjects who have smoked <math>< 5</math> pack years - at any time in the 3 months prior to admission to the quarantine unit they have used tobacco in any form (e.g.,

NO	STANDARD EXCLUSION CRITERIA
	smoking or chewing) or other nicotine-containing products in any form (e.g., gum, patch) or electronic cigarettes.
8.	Family history of 1st degree relative aged 50 years or less with sudden cardiac or unexplained death
9.	Family History of Severe COVID or response to any other viral disease e.g. Guillain–Barré
Measurements and investigations	
10.	A total body weight of $\leq$ 50g and a Body Mass Index (BMI) $\leq$ 18 kg/m  and $\geq$ 28 kg/m  . The upper limit of BMI may be increased to $\leq$ 30kg/m  at the PI's discretion, in the case of physically fit muscular individual
11.	Venous access deemed inadequate for the phlebotomy and cannulation demands of the study.
12.	Any clinically significant abnormal finding on screening biochemistry, haematology and microbiology blood tests or urinalysis i.e. grade 1 lab abnormalities (or above, see Appendix 4 Toxicity Grading Scale for Laboratory AEs) apart from minor deviations which are clinically acceptable and approved by the Principal Investigator 
 
a) Elevated random glucose.
 
b) Positive HIV, active/chronic hepatitis A, B or C test.
 
c) Confirmed positive test for drugs of abuse on admission and urinary cotinine at quarantine.
 

13.	A forced expiratory volume in 1 second (FEV1) and a forced vital capacity (FVC) <80% of predicted value calculated using ATS/ERS guidance
14.	Twelve-lead ECG recording with clinically relevant abnormalities as judged by the study physician/PI.
Recent respiratory infection	
15.	History of, or currently active symptoms suggestive of upper or lower respiratory tract infection (including reduced sense of taste and smell, raised body temperature and/or persistent cough) within 6 weeks prior to viral challenge.
16.	Presence of cold-like symptoms and/or fever (defined as subject presenting with a temperature reading of $>37.9^{\circ}\text{C}$ )
17.	History of previous SARS-CoV-2 infection at any time
Receipt of medications and interventions	

NO	STANDARD EXCLUSION CRITERIA
18.	Evidence of a live vaccine within 60 days prior to the planned date of viral challenge, a non-live vaccine within 30 days prior to the planned date of viral challenge (except for COVID-19 vaccines), or intention to receive any vaccination(s) before the day 28 follow-up visit.
19.	Receipt of blood or blood products, or loss (including blood donations) of 550 mL or more of blood during the 3 months prior to the planned date of viral challenge or planned during the 3 months after the final visit.
20.	
Medications
 
 
a) Use of any medication or product (prescription or over-the-counter), for symptoms of hayfever, nasal congestion or respiratory tract infections or dermatitis/eczema including the use of regular nasal or medium-high potency dermal corticosteroids, antibiotics and First Defence™ (or generic equivalents) within 7 days prior to the planned date of viral challenge apart from those described and allowed in Permitted Medication or agreed by the Principle Investigator
 
b) Receipt of any investigational drug within 3 months prior to the planned date of viral challenge.
 
c) Receipt of three or more investigational drugs within the previous 12 months prior to the planned date of viral challenge.
 
d) Prior inoculation with a virus from the same virus-family as the challenge virus.
 
e) Receipt of systemic (intravenous and/or oral) glucocorticoids or systemic antiviral drugs within 6 months prior to the planned date of viral challenge.
 
f) Over the counter medications (e.g. paracetamol or ibuprofen) where the dose taken over the preceding 7 days prior to the planned date of viral challenge had exceeded the maximum permissible 24-hour dose (e.g., >4g per day of paracetamol over the preceding week).
 
g) Use or anticipated use within 7 days prior to the planned date of viral challenge and during the conduct of the study of concomitant medications (prescription and/or non-prescription), including vitamins or herbal and dietary supplements within the specified windows.
 
h) Chronically used medications, vitamins or dietary supplements, including any medication known to be a moderate/potent inducer or inhibitor of cytochrome P450 enzymes, within 21 days prior to the planned date of viral challenge.
 
i) Subjects who have received any systemic chemotherapy agent, immunoglobulins, or other cytotoxic or immunosuppressive drugs at any time.
 

21.	Prior participation in another human viral challenge study in the preceding 12 months taken from the date of viral challenge in the previous study to the date of expected viral challenge in this study.
22.	Any nasal sampling procedure in the 6 months before date of expected viral challenge in this study. Nasal swabs are allowed.

NO	STANDARD EXCLUSION CRITERIA
General	
23.	Subject was mentally or legally incapacitated in the opinion of the Investigator.
24.	Females who: a) Are breastfeeding within 6 months of study commencement, or b) Had been pregnant within 6 months prior to the study, or c) Had a positive pregnancy test at any point during screening or prior to inoculation with challenge virus
25.	Those in close domestic contact (i.e. sharing a household with, caring for, or daily face to face contact) with children under 3 years, the elderly (>65 years), immunosuppressed persons, or those with chronic respiratory disease
Other	
26.	Was employed or was a first-degree relative of anyone employed by the Sponsor, a participating clinical trial site, or any Contract Research Organisation involved in the study.
27.	Any other reason that the Investigator considered made the subject unsuitable to participate.
28.	Participants with no knowledge of their family history

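### Exclusion 10 cannot be met as written: its weight unit is grams, its two BMI bounds are joined by 'and', and it leaves open whether low weight excludes on its own

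*Protocol*

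**What the plan says.** Protocol section 2.2, exclusion 10, sits under the sub-heading on measurements and investigations. It combines three conditions:

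- Total body weight at or below a limit printed in grams, joined by 'and' to the BMI condition: "50g and a Body Mass Index (BMI".
- A lower and an upper BMI bound, also joined by 'and': "18 kg/m 2 and $\geq$ 28 kg/m 2". The lower bound carries a 'less than or equal' sign.
- A discretion sentence for physically fit, muscular volunteers: "The upper limit of BMI may be increased to" a value written as at most 30 kg/m².

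The table header says how the list operates: "Any potential subject who meet any of the criteria below will be excluded from participating in this study". Section 3 has height and weight collected by webform, BMI by telephone, and height and weight again at the screening visit, but it gives no cut-off. The amendment summaries list changes to several other exclusion criteria and none to the weight and BMI item.

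**The concern.** An exclusion criterion is a decision rule, and staff must be able to apply it to a volunteer's height and weight and reach one answer. This rule has no possible positive case as printed, so it has to be repaired by whoever applies it. The repair is not unique. Restoring a plausible weight unit and treating the BMI bounds as two ends of a range still leaves the link between weight and BMI undefined.

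At stake is whether volunteers for a deliberate-infection study are selected by one consistent rule. The criterion is needed early: under section 3 a first visit is booked when the criteria are provisionally met on webform or telephone answers, which include height, weight and BMI. Two screeners could read the line differently and both believe they had followed it.

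**Working it through.** No sample size, power or error rate is involved. The check is one of logic, with BMI = weight in kg ÷ (height in m)².

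**1. The criterion as printed.** A person is excluded if weight ≤ 0.05 kg AND BMI ≤ 18 AND BMI ≥ 28.

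- No adult weighs 0.05 kg or less, so the first condition is never true.
- No number is both ≤ 18 and ≥ 28, so the second and third are never true together.

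Either fault alone empties the criterion. An enumeration over an assumed grid gives the same result. The grid has weights of 30 to 160 kg in 0.5 kg steps and heights of 1.40 to 2.10 m in 1 cm steps, keeping BMI between 12 and 50, which leaves 14,763 combinations. The criterion as printed excludes 0.

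**2. Partial repairs.**

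- Grams changed to kilograms, both 'and's kept: 0 excluded.
- BMI bounds read as alternatives, weight still in grams and joined by 'and': 0 excluded.

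So a 'k' lost in printing or in reading the PDF would not explain the problem.

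**3. Does the table header help?** It excludes anyone meeting any listed criterion. That is an 'or' between numbered items and does not change the 'and's inside item 10.

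**4. Full repairs do not agree.** Assume for illustration that kilograms were meant and that the BMI bounds are alternatives.

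| Reading | Grid cells excluded |
|---|---|
| Weight ≤ 50 OR BMI ≤ 18 OR BMI ≥ 28 | 10,787 |
| Weight ≤ 50 AND (BMI ≤ 18 OR BMI ≥ 28) | 1,313 |

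The BMI bounds alone, as alternatives, exclude 10,355 cells. Letting low weight exclude by itself therefore adds 10,787 − 10,355 = 432 cells, all at 50 kg or less with a BMI between the bounds. These are grid cells, not shares of any population.

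Two volunteers show the difference:

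- 48 kg, 1.55 m: 48 ÷ 1.55² = 48 ÷ 2.4025 ≈ 20.0. Excluded if weight stands alone; eligible if a BMI outside the range is also required.
- 60 kg, 1.85 m: 60 ÷ 1.85² = 60 ÷ 3.4225 ≈ 17.5. Excluded if BMI stands alone; eligible if low weight is also required.

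The second reading in the table has a further difficulty. A person of at most 50 kg reaches BMI 28 only at a height of at most √(50 ÷ 28) ≈ 1.34 m, so the upper bound would hardly ever act and the discretion sentence would have little to relax. That makes it unlikely for the upper bound. It does not settle the lower end, where weight and low BMI could still be meant jointly or separately.

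**5. The discretion clause.** The base bound excludes at 28 and above, so 28 itself is out. The relaxed bound is written as a permitted maximum, so 30 itself appears to be in. Put literally in place of the exclusion bound, 'at most 30' would reverse its direction.

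**The case against.** The strongest reply is that nobody would apply this line literally. A 50 g limit is absurd on its face. The sentence about raising the upper BMI limit makes sense only if 18 and 28 are the ends of a permitted range. Inclusion 6 requires good health as judged by the investigator, and exclusion 27 allows rejection for "Any other reason that the Investigator considered made the subject unsuitable to participate". A medical examination and a review of GP history also take place. This is a screening protocol: no one is inoculated under it, and entry needs separate consent under a main protocol that is not shown. Screening appointments are held at one organisation, so variation between sites is not in question.

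Most of this stands, and it limits the consequence. A reader might infer from the empty criterion that underweight or obese volunteers simply pass, or that some were admitted. The documents do not support that: other checks remain, and nothing shows how the line was applied. A reader might also call this a safety limit, but the protocol does not label it so.

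The reply does not remove the point. The other checks carry no weight or BMI figure, so they cannot stand in for the threshold. The inferred range settles how the two BMI bounds relate to each other, but not how weight relates to them. The two forms of the discretion limit can be understood as one boundary seen from opposite sides, which makes that part untidy rather than serious.

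**Conclusion.** The point holds as a drafting error in an operative eligibility threshold. As printed, exclusion 10 excludes nobody. As staff would probably read it, the two BMI bounds form a range, but the role of the weight limit is undetermined and the available readings select different volunteers. Volunteers at the low end are affected: those at or below the weight limit with a BMI inside the range, and those above it with a low BMI.

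How many volunteers this concerns cannot be estimated, because the protocol gives no distribution of height or weight and leaves the number recruited to the main study ("The number of subjects who are to be recruited will depend on specific sample-size requirements"). The examples assume that kilograms were intended, which the document does not state. Whether the same error stands in the main challenge-study protocol is unknown. A rewrite that simply made low weight a stand-alone exclusion would settle a question the text leaves open.

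**What to change.** Reconcile exclusion 10 with the corresponding line of the main challenge-study protocol, and correct that line too if it carries the same wording. The amended text should:

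1. correct the weight unit;
2. write the two BMI bounds as alternatives;
3. state explicitly whether the weight limit excludes on its own or only together with a BMI condition, and which one;
4. word the discretion clause in the same direction as the exclusion bound, so that the status of a BMI exactly at each limit is clear.

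The sponsor should confirm the thresholds; none is proposed here. The cost is a one-line amendment. No procedure is added, because height and weight are already collected.
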